7.2 Statistical Methods

Maps of stimulation locations corresponding to hand and arm muscle groups will be formed. The distance between the averaged positive nTMS stimulation sites for each type of motor response (APB, ADM, etc) and the corresponding averaged DCS site will be calculated, according to co-registered 3D coordinates in MRI anatomical space. For DCS, the center of the electrode eliciting motor response with the lowest current will be defined; when stimulation of several electrodes elicited motor response with the same minimum current, the average ECS site of these electrode centers will be used instead. The weighted mean of the DCS map will also be calculated.

The distance between the averages of nTMS and DCS maps, between the site eliciting a motor response with a minimum current and between the average of the nTMS map and the weighted average of the ECS map will be calculated.

The localizations will be also compared in relation to the patients' gyral anatomy. If the nTMS localization and the electrodes eliciting positive motor response in ECS activated the same gyrus, the localizations will be defined as anatomically concordant.

7.3 Subject Population(s) for Analysis

All subjects who complete the nTMS motor mapping session and later undergo direct cortical stimulation for functional mapping will be included in the analysis.

8. Safety and Adverse Events

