1.4 Research Risks & Benefits

1.4.1 Risks of Investigational Devices

Generally TMS is safe and well tolerated in both healthy subjects and neurological patients, as long as general safety recommendations are followed (Wasserman 1998). TMS applied as single pulse mode does not carry the risk of significant magnetic field exposure since the total stimulation time is short, and modulation of cortical excitability is highly unlikely. Single-pulse TMS does not cause any detrimental effects on EEG or cognitive and motor test performance (Bridgers and Delaney, 1989; Bridgers, 1991) and can be safely used in children (Eyre et al., 2001). According to a consensus statement on the safety of TMS (Rossi et al 2009), known side effects of TMS include transient headache (which occurs occasionally), syncope (mostly likely an epiphenomenon instead of relate to direct brain effect, which occurs rarely), local pain (rarely), neck pain (rarely), toothache (rarely) paresthesias (rarely); possible transient hearing changes (rarely) and possible malfunction of electric device only if TMS is delivered in close proximity with devices (rarely) (Rossi 2009). The overall incidence of these mild adverse events are thought to be approximately 5%, with headache being reported as the most common (Maizey 2013). Side effects are transient, and have not been reported to induce permanent neurological changes (Rossi et al 2009, Evans 2007).

The most serious possible side effect of TMS is that of an induced seizure. To date, there have been a total of 16 reports of seizures associated with TMS, of thousands of published studies. Previously the risk of inadvertently induces seizures is estimated to be less than 1 in 1000 rTMS procedures (which is considered a higher risk procedure than single pulse TMS as used in this protocol), a higher risk than most commonly prescribe antidepressants (O'Reardon et al 2005) In a safety review of TMS, Hallet et al (2007) report 3 seizures associated with single-pulse TMS since the 1998 safety guidelines were published for safe stimulation parameters. In first case, Haupt's et al (2004) report a generalized tonic clonic seizure in a patient with multiple sclerosis using single pulse TMS at 66% of TMS output. The authors suggested that the use of olanzapine and the underlying MS likely increased the patient's seizure risk. In the second case, Tharayil et al (2005) reported a generalized seizure in a patient with bipolar

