depression taking chlorpromazine and lithium, both medications known to increase seizure risk. To date, there has been a single report of an induced focal motor seizure during single pulse TMS of an epilepsy patient with a known epileptic focus in the left frontal cortex (Classen et al 1995). These few reported seizures were not associated with long term adverse outcome (Schrader et al. 2004).

In the event of a concurrent seizure during stimulation, one or more co-investigators with specialty training in epilepsy will be present to monitor for adverse effects and monitor for exacerbation of seizure type and frequency. If there is immediate cause for concern the PI and Co-PI will make necessary medical arrangements, including direction to the emergency room if needed. If any other unanticipated adverse events occur which are thought to be related to study intervention, the patient will be withdrawn from further participation in the study. Though our clinical trial will include a safety-monitoring plan, there are no known severe or lasting adverse effects with TMS using proper set-up.

1. Though minimal, due to the concern of potential increased seizures with TMS, we will monitor increase in seizure severity attributable to TMS by identifying all instances of generalized tonic clonic seizures after TMS treatments (defined as occurring within 20 minutes of stimulation). In addition, subjects will be asked to keep a seizure diary for the 7 days prior to stimulation, and the 7 days after stimulation. Instances where seizure frequency increased after TMS will be reported to the IRB within 1 week.
2. If a self-limited, short (<5 min) complex partial seizure or evolution into generalized tonic clonic seizures occur during the procedure, TMS mapping will stop for that day.
3. In case of, pain, transient hearing impairment, the patient's primary epileptologist will be notified and appropriate medical followup will be arranged.
4. If any other unanticipated adverse events occur, the patient will be withdrawn from further participation in the study.

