2.2 Secondary Objective(s)

This trial is also designed to detect safety and tolerability of nTMS in epilepsy patients.

3 Study Design

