3.1.1 Baseline clinical visit and seizure diary

We will enroll 14 patients who will undergo epilepsy surgery with expected subdural grid coverage over primary motor cortex. Potential subjects will be identified at the weekly multi-disciplinary epilepsy conference. Subjects must have a recent (<2 years) MRI scan, and registration of the TMS coil to the MRI scan via the Brainsight neuronavigation system will be utilized to guide TMS coil placement (Gugino et al 2001). When a presurgical fMRI is available which demonstrates the patient's hand knob, the fMRI will be used with the Brainsight neuronavigation system. Subjects will be recruited and consented during a presurgical clinical visit where the patient's primary epileptologist will introduce members of the research team.

Patients will be asked to keep a 7 day seizure diary prior to the TMS session.

3.1.2 nTMS mapping

Patients will receive a session of single-pulse TMS mapping of the motor area, at the outpatient TMS clinic at NYU Neurology Ambulatory Care Center, at [name] prior their epilepsy surgery, according to the following procedures:

- a. Determination of the motor threshold by (1) finding the most excitable region in the hand knob which elicits the strongest compound muscle action potential (CMAP) in the APB muscle; (2) finding the motor threshold by determining output stimulation intensity which generates peak to peak CMAP response above 50 mV in 5/10 stimulation cycles (Rossini et al., 1994).
- b. Concurrent EMG will be measured with electrodes placed at APB, abductor digiti minimi, flexor carpi radialis muscles. Reference electrode will be placed at the ipsilateral elbow above the brachial biceps muscle.
- c. Mapping of the upper extremity. After determination of the MT, mapping of the UE will be performed at 110% of the rMT. All positive and negative stimulation sites will be recorded and saved.

Patients will be closely monitored during TMS stimulation. Each subject will have a complete neurological examined by a neurologist before and immediately after nTMS. Patients will also be provided a side effects questionnaire after TMS mapping. Patients will then be asked to keep a 7 day seizure diary after the nTMS session

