3.3 Secondary Study Endpoints

In addition, this study is designed to detect safety and tolerability of TMS in the epilepsy patient, as measured by 7 day seizure diaries before and after the nTMS sessions.

4 Subject Selection and Withdrawal

We will recruit 14 patients, aged 12-60 years, who will have motor mapping and epilepsy surgery. Because nTMS is expected to most benefit pediatric patients, we plan to enroll at least 4 subjects under the age of 17, to establish validity in this population. There will be no restrictions on race or ethnicity.

Safety and tolerability in healthy volunteers is established for TMS in previous studies, and therefore healthy controls will not be necessary. However side effect questionnaire will be provided after TMS mapping.

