7.1 Sample Size Determination

We estimate 10 subjects total necessary to detect a 50% difference between nTMS and DCS mapping, assuming alpha 0.05 and power 0.8. However, given the possibility of subject dropout, and the unknown nTMS side-effect profile and seizures we propose to add ~1/3 to total patient enrollment, and thus will enroll 14 patients. We plan to enroll at least 4 children ages 12-17 years, to assess for the validity of nTMS in a pediatric population, which is expected to benefit the most from this procedure.

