8.1 Definitions

Unanticipated Problems Involving Risk to Subjects or Others

Any incident, experience, or outcome that meets all of the following criteria:

- Unexpected in nature, severity, or frequency (i.e. not described in study-related documents such as the IRB-approved protocol or consent form, the investigators brochure, etc)
- Related or possibly related to participation in the research (i.e. possibly related means there is a reasonable possibility that the incident experience, or outcome may have been caused by the procedures involved in the research)
- Suggests that the research places subjects or others at greater risk of harm (including physical, psychological, economic, or social harm).

Unanticipated Adverse Device Effect

An Unanticipated Device Effect is any serious adverse effect on health or safety, or any life-threatening problem or death caused by, or associated with a device, if that effect, problem, or death was not previously identified in nature, severity, or degree of incidence in the investigational plan or application (including a supplementary plan or application), or any other unanticipated serious problem associated with a device that relates to the rights, safety, or welfare of subjects.

Serious injury

Any injury or illness that is any one of the following:

- life-threatening
- results in permanent impairment of a body function or permanent damage to body structure
- necessitates medical or surgical intervention to preclude permanent impairment of a body function or permanent damage to a body structure

Adverse Event

(a) In parallel with recording the primary outcome, we will monitor for increase in seizure severity attributable to TMS by identifying all instances of generalized tonic clonic seizures after TMS treatments. Instances where seizure frequency increased after TMS will be reported to the IRB within 72 hours.

(b) If a self-limited, short (<5 min) partial seizure or evolution into generalized tonic clonic seizure occur, TMS mapping will stop for that day.

(c) If a secondarily generalized (convulsion starting in one area of body and then spreading to other areas) or 2 partial seizures occur during treatment, the patient will be withdrawn from further participation in the study.

(d) If any other unanticipated adverse events occur, the patient will be withdrawn from further participation in the study.

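### Section 7.3 gives one analysis population, tied to completed nTMS and later DCS, without limiting it to mapping; the secondary safety endpoint has no set, denominator or group summary

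*Combined protocol and SAP*

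**What the plan says.** **Objective and endpoint.** Section 2.2 states: "This trial is also designed to detect safety and tolerability of nTMS in epilepsy patients". Section 3.3 says how: "this study is designed to detect safety and tolerability of TMS in the epilepsy patient, as measured by 7 day seizure diaries", kept before and after the session. Section 3.1.2 adds a tolerability instrument: "Patients will also be provided a side effects questionnaire after TMS mapping".

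**Analysis.** Section 7.2 covers distances between nTMS and DCS sites and agreement by gyrus, and nothing on diaries, side effects or adverse events. Section 7.3 is a single sentence: "All subjects who complete the nTMS motor mapping session and later undergo direct cortical stimulation for functional mapping will be included in the analysis". It names two conditions, a completed session and later DCS, and no endpoint.

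**Safety conduct.** Section 1.4.1 (item 1) commits to "identifying all instances of generalized tonic clonic seizures after TMS treatments (defined as occurring within 20 minutes of stimulation"), sets up the diaries, and has increases in seizure frequency after TMS reported to the IRB. Section 8.1(a) repeats the monitoring commitment. Section 8.2 has all adverse device effects recorded, 8.5 has their number and type assessed regularly, and 10.1 has all adverse events scored for severity and relationship. None of these is restricted to subjects who go on to DCS.

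**Withdrawal.** Section 8.1(c) withdraws a subject who has a secondarily generalized seizure or two partial seizures during treatment; 8.1(d) does so for any other unanticipated adverse event.

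**Sample size.** Section 7.1 raises enrolment from 10 to 14: "given the possibility of subject dropout, and the unknown nTMS side-effect profile and seizures we propose to add ~1/3 to total patient enrollment".

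**The concern.** The conditions in 7.3 suit a comparison of two maps, since a subject without both maps contributes nothing to it. They do not suit a safety summary. The questionnaire and both diaries can be complete in a subject who never has DCS. The first condition, completing the session, can also fail because of the very events that the secondary endpoint is meant to capture.

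Two effects should be kept apart. Losing subjects withdrawn in session would remove some of the most severe events from the reported rate, which favours a conclusion that nTMS was tolerated. Losing subjects who had no DCS mainly discards valid data and widens the interval, with no expected direction if having DCS is unrelated to tolerability.

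There is a smaller consequence for mapping. Results from completed sessions alone do not show how often a session was started and not finished, which matters in a feasibility study.

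**Working it through.** **Step 1: two readings of 7.3.**

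- *It governs every analysis.* Safety is then summarised only in subjects who completed nTMS and had DCS.
- *It governs mapping only, because it follows 7.2.* Safety then has no stated population, denominator or group summary.

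The safety endpoint is incompletely specified on either reading. Only the first can produce a biased summary.

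**Step 2: who can fall outside 7.3 although stimulated.**

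- Subjects withdrawn under 8.1(c) or (d) before mapping is finished.
- Subjects who finish mapping but do not undergo DCS, for whatever reason.

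A worse diary after the session, or a seizure after a finished session, does not by itself put anyone outside.

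**Step 3: the plan's own allowance (7.1).** 10 × (1 + 1/3) = 13.3, rounded up to 14, which reproduces the stated enrolment. The allowance is 14 − 10 = 4 subjects. It covers losses for any reason, including before stimulation, so 4 is an extreme value for stimulated subjects lost and not an expected one.

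**Step 4: one in-session withdrawal (illustration).** Assume that all 14 are stimulated, one is withdrawn in session before mapping is finished, and the other 13 complete mapping, have DCS and have no such event. Intervals are exact (Clopper-Pearson), two-sided 95%.

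- All stimulated: 1/14 = 7.1%. Lower limit 1 − 0.975^(1/14) = 0.002. The upper limit solves (1 − p)^14 + 14p(1 − p)^13 = 0.025, giving 0.339. Interval 0.2% to 33.9%.
- 7.3 set: 0/13. Upper limit 1 − 0.025^(1/13) = 0.247. Interval 0 to 24.7%.

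**Step 5: loss through the DCS condition alone (illustration).** Assume that no events occur and compare upper limits, 1 − 0.025^(1/n).

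| Subjects counted | Exact upper 95% limit with no events |
|---|---|
| 14 | 23.2% |
| 13 | 24.7% |
| 10 (all 4 losses after stimulation) | 30.8% |

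Section 1.4.1 gives roughly 5% as the general incidence of mild effects. If that rate applied here and were unrelated to having DCS, the chance of seeing at least one event would be 1 − 0.95^14 = 51.2% with 14 subjects and 1 − 0.95^10 = 40.1% with 10. This part widens the interval; it does not flatter the result.

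**The case against.** The strongest reply is that 7.3 was never meant for safety. It requires DCS, follows methods that concern only maps, precedes a separate safety chapter, and says who is included without saying that nobody else is. Section 8.1(a) treats seizure monitoring as an activity alongside the mapping: "we will monitor for increase in seizure severity attributable to TMS by identifying all instances of generalized tonic clonic seizures after TMS treatments". On that reading there is no selection bias, only an unstated denominator and summary. In a 14-subject feasibility study with no safety hypothesis test, that is a modest gap. This much stands: the bias is conditional on how 7.3 is applied. The safety provisions do not close the gap, however, because they ensure that an event is known and not that it enters a reported rate.

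Three stronger readings are tempting, and the documents do not support them.

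- *Safety events in excluded subjects would go unrecorded or unreported.* Sections 8.1(a), 8.2, 8.5 and 10.1 say otherwise.
- *Every subject with a serious in-session seizure is necessarily excluded.* Completing the session is not defined. Section 8.1(c) ends further participation without saying that the session counts as incomplete, and a qualifying seizure could come after the last site is mapped. DCS is routine care, so withdrawal does not itself prevent it. Such subjects can be left out; it is not certain that they would be.
- *The plan has no safety measure at all.* Sections 1.4.1 and 3.3 name a before/after diary measure and a 20-minute seizure window. What is missing is the analysed set, the denominator and the group summary.

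**Conclusion.** The point holds in this limited form. Section 7.3 states one population without confining it to mapping, and no analysed set, denominator or group summary is given for the secondary safety endpoint. Applied as written to safety, the rule can omit subjects withdrawn before mapping is finished, in the direction of apparent tolerability, and omits subjects without DCS at a cost in precision.

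The number affected cannot be derived from the documents. The change from 1/14 to 0/13 rests on a single hypothetical subject and the two intervals overlap widely; the change in upper limit from 23.2% to 30.8% is the extreme case. Both show direction and scale and neither is a forecast. The gap is worth closing because it affects a stated objective and the remedy is cheap. It does not undermine the mapping comparison.

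**What to change.** 1. State in 7.3 that the population applies to the nTMS-DCS mapping comparison only.
2. Add a safety set of all subjects who receive at least one TMS pulse. Summarise in it, descriptively, seizures in session and within 20 minutes, recorded adverse effects, questionnaire results, and the available pre- and post-session diaries with the number missing. At this sample size a subject listing would serve as well as a table.
3. Beside the mapping results, report the number of sessions attempted but not completed, with reasons.

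The cost is protocol wording and one table or listing, with no extra patients. Diaries may be missing for withdrawn subjects, so the before/after comparison may remain incomplete, and the reported safety figures may be slightly less favourable.

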8.1 Definitions

Unanticipated Problems Involving Risk to Subjects or Others

Any incident, experience, or outcome that meets all of the following criteria:

- Unexpected in nature, severity, or frequency (i.e. not described in study-related documents such as the IRB-approved protocol or consent form, the investigators brochure, etc)
- Related or possibly related to participation in the research (i.e. possibly related means there is a reasonable possibility that the incident experience, or outcome may have been caused by the procedures involved in the research)
- Suggests that the research places subjects or others at greater risk of harm (including physical, psychological, economic, or social harm).

Unanticipated Adverse Device Effect

An Unanticipated Device Effect is any serious adverse effect on health or safety, or any life-threatening problem or death caused by, or associated with a device, if that effect, problem, or death was not previously identified in nature, severity, or degree of incidence in the investigational plan or application (including a supplementary plan or application), or any other unanticipated serious problem associated with a device that relates to the rights, safety, or welfare of subjects.

Serious injury

Any injury or illness that is any one of the following:

- life-threatening
- results in permanent impairment of a body function or permanent damage to body structure
- necessitates medical or surgical intervention to preclude permanent impairment of a body function or permanent damage to a body structure

Adverse Event

(a) In parallel with recording the primary outcome, we will monitor for increase in seizure severity attributable to TMS by identifying all instances of generalized tonic clonic seizures after TMS treatments. Instances where seizure frequency increased after TMS will be reported to the IRB within 72 hours.

(b) If a self-limited, short (<5 min) partial seizure or evolution into generalized tonic clonic seizure occur, TMS mapping will stop for that day.

(c) If a secondarily generalized (convulsion starting in one area of body and then spreading to other areas) or 2 partial seizures occur during treatment, the patient will be withdrawn from further participation in the study.

(d) If any other unanticipated adverse events occur, the patient will be withdrawn from further participation in the study.

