4.4 Early Withdrawal of Subjects

4.4.1 When and How to Withdraw Subjects

This study is expected to end after all participants have completed all visits, and all information has been collected. Under the following circumstances the subject's participation will be terminated by the investigator without regard to the participant's consent:

- The subject not able to attend the study visits required by the study.
- The subject fails to follow the study requirements.

- If a subject becomes pregnant.
- If a subject decides not to continue participation in the study (by choice)

5 Study Device

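### Three separate safety provisions are each inconsistent within themselves: the action after a partial seizure that generalizes during mapping, the IRB deadline for a seizure increase, and the section 8.3.1 reporting deadline

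*Combined protocol and SAP*

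**What the plan says.** **Seizure during mapping.** Section 8.1, Adverse Event, item (b) provides that if a self-limited partial seizure shorter than 5 minutes or "evolution into generalized tonic clonic seizure occur, TMS mapping will stop for that day". Item (c) begins "c) If a secondarily generalized (convulsion starting in one area of body and then spreading to other areas" and continues "or 2 partial seizures occur during treatment, the patient will be withdrawn from further participation in the study". Section 1.4.1, item 2, repeats the first rule: "complex partial seizure or evolution into generalized tonic clonic seizures occur during the procedure, TMS mapping will stop for that day". Its list has no counterpart to item (c). Section 4.4.1 lists four circumstances in which "participation will be terminated by the investigator without regard to the" participant's consent. They are inability to attend visits, failure to follow study requirements, pregnancy, and the subject's own choice.

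**Increase in seizure frequency.** Section 8.1, item (a): "Instances where seizure frequency increased after TMS will be reported to the IRB within 72 hours". Section 1.4.1, item 1: "Instances where seizure frequency increased after TMS will be reported to the IRB within 1 week". The same item 1 says that "subjects will be asked to keep a seizure diary for the 7 days prior to stimulation, and the 7 days after stimulation".

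**Unanticipated problems and unanticipated adverse device effects.** In section 8.3.1 the heading allows 5 working days. The sentence directly under it allows 10 working days from the investigator's awareness and introduces the same list. A second list, of other reportable events, has its own sentence with 10 working days. Section 10.1 requires serious and unexpected adverse events to reach the IRB and the monitoring committee within 72 hours. Section 8.5.1 refers the reader to section 8.3.1 only.

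**The concern.** Section 1.4.1 ranks an induced seizure as the gravest risk of TMS. Every subject has epilepsy, the age range is 12 to 60, and at least 4 of the 14 planned subjects are to be minors. The rules for this event should be readable in one way only.

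As written, two investigators who each follow the protocol could differ in two respects. After a partial seizure that generalizes, one could keep the subject in the study and the other could withdraw the subject. After an increase in seizures, one could report on day 2 and the other on day 6. The first difference may also affect data. Section 3.3 measures safety by the diaries before and after the session, and section 7.3 analyses subjects who complete mapping and later have direct cortical stimulation. Whether a seizure leads to withdrawal could therefore affect who contributes to either.

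The section 8.3.1 conflict mainly concerns other, unexpected events, because the documents already describe induced seizure as a known risk.

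**Working it through.** The plan gives no statistical figure to reproduce here. The check sets the texts side by side; the only arithmetic is on the time limits.

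**1. Seizure during mapping.** Take as a test event a self-limited partial seizure of under 5 minutes that begins in one body part and spreads to a generalized convulsion during the session.
- 8.1(b): applies, because it names evolution to a generalized seizure. Action: stop for the day. It is silent on study status.
- 8.1(c): applies, because the event fits the explanation in its parentheses. Action: withdrawal.
- 1.4.1, item 2: applies. Action: stop for the day only.
- 4.4.1: 0 of 4 circumstances is a seizure, so it does not settle the matter.
- The closing items in 1.4.1 and 8.1 withdraw a patient for any other unanticipated event. A seizure is anticipated and has its own items, so these do not settle it either.

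Limiting (b) to short events does not remove the overlap, because (c) has no duration limit. The shared action is stopping that day. The open question is study status.

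**2. Increase in seizure frequency.** 1 week = 7 x 24 = 168 hours, and 168 - 72 = 96 hours = 4 days. The gap is the same for any common clock start. A report at 100 hours fails section 8.1 (100 > 72) and meets section 1.4.1 (100 < 168). Neither sentence says whether time runs from the session, from the change in seizures, or from the investigator's awareness. The start needs defining because an increase between two 7-day diaries is a comparison and has no single date of onset.

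**3. Section 8.3.1.** 10 / 5 = 2, so one limit is twice the other for one list. A report on working day 8 breaks the heading (8 > 5) and meets the sentence under it (8 < 10). The list of other reportable events has its own 10-day sentence, so it does not account for the 10 days under the 5-day heading. The 72 hours in section 10.1 has no clock start and covers part of the same ground. It can be met together with either longer limit, so it is an overlap that needs reconciling.

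**4. Related text.** Sections 8.4 and 10.1 both list events that may prompt a study pause. Section 8.4 names worsening of seizure intensity or frequency, whereas section 10.1 names simply a seizure. Both are discretionary, but the triggers differ.

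**The case against.** The strongest reply is that nobody is forced to break one rule in order to obey another. Reporting at the shortest limit meets every deadline. Items (b) and (c) can be read as escalating steps: stop for the day, then also withdraw in the more serious cases. The plan describes a single mapping session, so the practical gap is narrow. Section 1.4.1 describes risks and need not restate every withdrawal rule. Section 8.3.1 presents itself as an account of the institution's IRB requirements and defers to the IRB of record.

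Much of this stands. The limits can be met together, and (b) and (c) share the same-day stop. It does not dispose of the point. Item (b) itself names the generalized event, so the text does not establish an escalating order. Nothing says that the shortest limit governs or that section 8.1 prevails over section 1.4.1. Deference to an IRB does not explain two limits for one list.

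Three stronger readings are tempting and are not supported:
- A reader might infer that the three provisions contradict one another. They are unrelated; each is inconsistent only within itself.
- A reader might infer that withdrawal ends the post-session diary and the post-operative visit. The documents do not say which data collection stops. Section 8.2 requires adverse device effects to be followed to resolution or stabilization, and section 6.3 ties the visit to regular clinical care.
- A reader might infer that an increase appearing late in the diary would be overdue before it arose. That needs a clock starting at the session, which no section states.

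**Conclusion.** The concern holds as three separate inconsistencies in the current text.

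1. One seizure event falls under two rules in section 8.1 and under only one of them in section 1.4.1. Whether the subject remains in the study is unresolved. Any effect on later data collection is possible but not established.
2. One report to the IRB has limits of 72 and 168 hours, 96 hours apart from any common start, with no start stated.
3. One list in section 8.3.1 has limits of 5 and 10 working days, with a further 72-hour overlap from section 10.1.

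The first conclusion assumes that a partial seizure evolving into a generalized tonic clonic seizure is the secondarily generalized seizure explained in item (c), which that item's own wording supports. The sample size of 10, enrolled as 14, and the primary analysis formulas are unaffected. The text should still be corrected, because the first two conflicts govern the event that the protocol treats as its main risk.

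**What to change.** Amend the protocol so that each event has one subject-level action and one reporting deadline with a stated clock start:
- Reconcile sections 1.4.1 and 8.1 on the action after a seizure during mapping and on the deadline for an increase in seizure frequency.
- Reconcile sections 8.3.1, 8.5.1 and 10.1 on the deadlines for unanticipated and for serious unexpected events.
- Keep each rule in one place and replace duplicates with cross-references, including one from section 4.4.1 to the final seizure rule.
- State which data collection continues after withdrawal.
- Check the study-pause triggers in sections 8.4 and 10.1 for consistency.

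The sponsor and the IRB decide which action and which deadlines stand; this review does not propose them. The cost is amendment wording only, with no new procedures.
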